ZBI	Zarit Burden Interview

1 INTRODUCTION

This statistical analysis plan (SAP) provides a technical and detailed elaboration of the summaries of efficacy and safety data. Specifications for tables, figures, and listings are contained in a separate document.

Enrollment in the study was terminated early by the sponsor for business reasons not related to the safety of pimavanserin after 111 subjects were randomized. The last subject was randomized into the study on November 2, 2017. As a result, the study is not powered to definitively evaluate efficacy measures and the summaries will be descriptive in nature. No hypothesis testing is planned.

2 OBJECTIVES

The purpose of this study is to evaluate the safety and efficacy of pimavanserin at doses (free base) of 34 mg and 20 mg, compared with placebo in the treatment of agitation and aggression in subjects with probable Alzheimer's disease (AD).

2.1 Primary Objective

The primary objective of the study is to evaluate the efficacy of pimavanserin compared with placebo in the treatment of agitation and aggression after 12 weeks.

2.2 Secondary Objective

The secondary objective of the study is to evaluate the efficacy of pimavanserin compared with placebo on caregiver burden.

2.3 Exploratory Objectives

Exploratory objectives of the study are:

- To evaluate the efficacy of pimavanserin compared with placebo for the following:
 - Clinician's global assessment of treatment benefit
 - Other neuropsychiatric symptoms
 - Functional status
 - Sleep and daytime wakefulness
 - Cognition
 - Need for rescue medication
- To evaluate the safety and tolerability of pimavanserin
- To evaluate the plasma concentrations of pimavanserin and the major metabolite AC-279

3 STUDY DESIGN

3.1 General Study Design

This study will be conducted as a Phase 2, 12-week, randomized, double-blind, placebo-controlled, multicenter, outpatient study in subjects with a diagnosis of probable AD, according to the National Institute on Aging-Alzheimer's Association (NIA-AA) guidelines who have clinically significant agitation/aggression and who meet the following criteria:

- Mini-Mental State Examination (MMSE) score of 5 to 26 (inclusive) at the Screening Visit
- Neuropsychiatric Inventory-Clinician Rating Scale (NPI-C) combined agitation and aggression domain score of ≥ 14 at both the Screening and Baseline visits

The original planned sample size was approximately 432. For business reasons, not related to safety, the enrollment (randomization) of new subjects into the study was stopped after 111 subjects were randomized. The last subject was randomized into the study on November 2, 2017. On the first day of the randomized treatment phase (Baseline), eligible subjects were randomly assigned to receive pimavanserin 34 mg per day, pimavanserin 20 mg per day, or placebo daily in a 1:1:1 ratio, according to a computer-generated randomization schedule. The randomization was stratified according to geographic region (North America, Europe, or Rest of World).

[figure not shown]
The duration of participation for individual subjects will be up to approximately 20 weeks. Each subject will participate in a 2- to 4-week screening period, a 12-week treatment period, and a 30-day safety follow-up (telephone call) for those subjects who discontinue prematurely from the study or who do not enroll in the open-label extension study (Study ACP-103-033). The end of the clinical trial will be when the last subject completes the last scheduled assessment (i.e., 30-day follow-up or enrolled in the extension study).

[Figure 1](#) illustrates the study design.

3.2 Schedule of Assessments

The schedule of events and assessments for the study is presented in [Table 1](#).

Figure 1 Study Design

^a For subjects taking antipsychotic medication, the screening period may be extended to 4 weeks if necessary for wash-out of at least 5 half-lives of the medication.

AD = Alzheimer's disease; NIA-AA = National Institute on Aging-Alzheimer's Association; QD = once daily

Table 1 Schedule of Assessments

Procedure	Visit Number	Screening Period	Treatment Period					Follow-Up
			Visit 1 ^a Baseline (1)	Visit 2 ^a Week 2 (15)	Visit 3 ^a Week 4 (29)	Visit 4 ^a Week 8 (57)	Visit 5 ^a (EOS/ET) Week 12 (85)	
Visit Week (Day)	Week -2 to -4 ^b							Visit 6 ^a Week 16 (~115)
Allowable visit window (# days)	NA		NA	±3	±3	±3	±3	+7
Clinic (C) or Telephone (T) Visit	C		C	C	C	C	C	T
Informed consent	X							
Inclusion/exclusion criteria assessment	X		X ^d					
Medical history and demographics	X							
Alzheimer's disease history	X							
Physical examination	X							X
Vital signs (including height ^e and weight)	X		X	X	X	X	X	X
ECG ^f	X		X		X			X
Clinical laboratory tests ^g	X		X		X			X
Pregnancy test ^h	X		X		X			X
PK sampling			X	X ⁱ	X			X
CMAI			X	X	X	X		X
ZBI			X	X	X	X		X
NPI-C (Agitation and Aggression Domains)	X ^j		X	X	X	X		X
NPI-C (All Remaining Domains)			X					X
MMSE	X		X		X	X		X
mADCS-CGIC			X	X	X	X		X
KSS			X	X	X	X		X
ADCS-ADL			X					X
MRI or CT ^k	X							
Psychosocial therapy	X							
Assessment of concomitant medications/treatments	X		X	X	X	X	X	X
Assessment of adverse events ^l	X		X	X	X	X	X	X
GCAS	X		X	X	X	X	X	X
Randomization			X					
Dispense study drug			X		X	X		
Study drug administration at the clinic ^m			X					
Study drug accountability					X	X	X	

Abbreviations: AD = Alzheimer's Disease; ADCS-ADL = Alzheimer's Disease Cooperative Study-Activities of Daily Living Inventory; C = clinic visit; CMAI = Cohen-Mansfield Agitation Inventory; CT = computed tomography; ECG = electrocardiogram; EOS = end of study; ET = early termination; GCAS=Global Clinician Assessment of Suicidality; KSS = Karolinska Sleepiness Scale; MMSE = Mini-Mental State Examination; mADCS-CGIC = modified Alzheimer's Disease Cooperative Study – Clinical Global Impression of Change; MRI = magnetic resonance imaging; NA = not applicable; NPI-C = Neuropsychiatric Inventory-Clinician Rating Scale; PK = pharmacokinetic; ZBI = Zarit Burden Interview

- a. Study visits are designated by weeks and have a ± 3 -day window (Visits 2 through 5) or a $+7$ -day window (Visit 6) calculated from the Baseline Visit (Day 1). Clinic visits may be split over multiple days within the specified windows, if necessary.
- b. The screening period must be at least 2 weeks long and no more than 4 weeks long.
- c. For subjects who discontinue prematurely from the study or who do not enroll in the open-label extension study, a follow-up safety assessment will be conducted by telephone call approximately 30 days after the last dose of study drug.
- d. NPI-C combined agitation and aggression domain score and wash-out of prohibited medications are the only eligibility assessments required at both Screening and Baseline (Day 1). All other eligibility criteria are to be established during Screening.
- e. Height is assessed as part of the vital sign measurement only at the Screening Visit; weight will be assessed at every clinic visit as part of the vital sign measurements.
- f. 12-lead ECG to be completed in triplicate at screening and single read at subsequent visits. ECGs can be performed any time before blood sampling or at least 30 minutes after blood sampling during clinic visits.
- g. Urinalysis requirement not applicable to subjects who are unable to provide urine sample (e.g., incontinent subjects).
- h. A serum pregnancy test should be performed at the initial screening visit. A urine pregnancy test should be performed at Baseline (Day 1), Week 4, and Week 12 (EOS/ET) for female subjects of childbearing potential.
- i. Note: If collection at Week 2 does not occur, then collection should be attempted at Week 8.
- j. Only the agitation and aggression domain will be completed at the Screening Visit.
- k. MRI or CT must be obtained during or subsequent to diagnosis of probable AD, or during the screening period (prior to Baseline).
- l. Any untoward medical occurrence that occurs after signing the informed consent form (i.e., during the screening period) should be recorded as an adverse event, even if dosing has not begun.
- m. The first dose of study drug must be administered to the subject at the clinic only after all Baseline assessments are performed, including the blood sampling for PK assessment. If any Baseline assessments extend to an additional day, the first dose of study drug will be administered at completion of assessments on this day.

3.3 Randomization

On Day 1 of the treatment phase, eligible subjects who meet all inclusion and none of the exclusion criteria will receive pimavanserin 34 mg per day, pimavanserin 20 mg per day or daily placebo according to a computer-generated randomization schedule. Subjects will be randomized in a 1:1:1 ratio to 1 of 3 treatment groups (pimavanserin 34 mg, pimavanserin 20 mg, or placebo), and stratified according to geographic region (North America, Europe, or Rest of World).

3.4 Blinding

Treatment assignment will be double-blind such that neither the subjects, study partners/caregivers, sponsor personnel who oversee the study, nor the Investigator and study personnel will know which treatment is assigned to each subject.

3.5 Determination of Sample Size

The original planned sample size was approximately 432. For business reasons, not related to safety, the enrollment (randomization) of new subjects into the study was stopped after 111 subjects were randomized. The last subject was randomized into the study on November 2, 2017. Thus, this study is not powered to definitively evaluate efficacy measures and only descriptive summaries will be provided.

4 ANALYSIS SETS

Randomized Analysis Set

The Randomized Analysis Set will consist of all subjects who were randomized.

Subjects will be classified according to the randomized treatment assignment.

Safety Analysis Set

The Safety Analysis Set will consist of a subset of subjects in the Randomized Analysis Set who received at least one dose of study drug.

Subjects will be classified according to the actual treatment received.

Full Analysis Set

The Full Analysis Set will consist of a subset of subjects in the Safety Analysis Set who have both a Baseline value and at least 1 post-Baseline value for the CMAI total score.

Subjects will be classified according to the randomized treatment assignment.

Per-protocol Analysis Set

The Per-protocol Analysis Set will consist of a subset of subjects in the Full Analysis Set who do not have any protocol deviation which is considered to have substantial impact on the primary efficacy outcome, change from Baseline to Week 12 in the CMAI total score. The precise reasons for excluding subjects from the Per-protocol Analysis Set will be fully defined and documented *a priori* before the clinical database lock.

Subjects will be classified according to the randomized treatment assignment.

Pharmacokinetics Analysis Set

The Pharmacokinetics Analysis Set will consist of subjects with at least one measurable pimavanserin plasma concentration.

Subjects will be classified according to the actual treatment received.

5 DATA HANDLING CONVENTIONS

All data collected in the study will be listed.

5.1 General Data Reporting Conventions

For continuous variables, the following summary statistics will be provided: number of subjects, mean, standard error of the mean (SE), standard deviation (SD), minimum, maximum and median. Unless specified otherwise, means, medians, and confidence intervals (CIs) will be presented to one more decimal place than the raw data, and the standard deviations and standard errors will be presented to 2 more decimal places than the raw data. Unless specified otherwise, all confidence intervals will be 2-sided 95% confidence intervals.

For categorical variables, summaries will include the number and percentage of subjects in each category, using the number of subjects with non-missing values as the denominator for the percentages (unless otherwise specified). Categories with zero counts will not have zero percentages displayed. Percentages will be presented with 1 decimal place.

When converting number of days to months, it will be calculated by dividing the number of days by 365.25 and then multiplying by 12. When converting number of days to years, the number of days will be divided by 365.25.

5.2 Derived Variables

In general, assessment total scores and subscale scores will be derived within the analysis datasets. In the event that total scores and/or subscale scores are also collected on the electronic case report form (eCRF), the derived values will be used for all summaries. Both the raw and derived scores will be presented in listings.

5.2.1 Cohen-Mansfield Agitation Inventory Long-form (CMAI)

The CMAI is assessed at Baseline, and Weeks 2, 4, 8 and 12/ET visits.

The CMAI is a 29-item scale designed to systematically assess agitation, rated on a 7-point (1-7) scale of frequency (1 = Never; 2 = Less than once a week; 3 = Once or twice a week; 4 = Several times a week; 5 = Once or twice a day; 6 = Several times a day; 7 = Several times an hour). Subjects are rated by their primary caregiver regarding the frequency with which they manifest physically aggressive, physically non-aggressive, and verbally agitated behaviors. The CMAI in this study is to be completed by interview of the caregiver. Ratings are inclusive of the 2 weeks prior to the administration of the scale.

In addition to the 7-point frequency scale, there are two other options for rating the behavior: 1) “8 - would occur if not prevented” (e.g., a person is physically restrained so he/she cannot pace), and 2) “9 - not applicable” (e.g., a non-verbal resident not being able to repeat sentences or questions, or a person who cannot walk or move a wheelchair not being able to pace, an amputated person not being able to kick). These two ratings are used only if the behavior really has never occurred in the past two weeks. If it has occurred, then the 1-7 point frequency scale should be used. These ratings of 8 and 9 are not included in the CMAI total score calculation. The CMAI has a range of 29-203 points, with higher scores indicating more severe agitation symptoms. If there are less than 6 missing items then the total score will be imputed by replacing each missing item with the mean (rounded to the nearest integer) of the non-missing values for that subject and timepoint. If there are more than 5 missing items then the total score will be missing.

In addition to the total score, behavioral subscales will be defined as follows ([Rabinowitz et al, 2005](#)):

- Aggressive Behavior: 12 Items (minimum = 12, maximum = 84)
- Sum of scores from items 3, 4, 7, 8, 9, 10, 11, 13, 14, 15, 21 and 25
- Physically Non-aggressive Behavior: 6 Items (minimum = 6, maximum = 42)
- Sum of scores from items 1, 2, 16, 22, 26, and 29
- Verbally Agitated Behavior: 4 Items (minimum = 4, maximum = 28)
Sum of scores from items 5, 6, 18, and 19
- Hiding and Hoarding : 2 Items (minimum = 2, maximum =14)
Sum of score from items 23 and 24

For the aggressive behavior subscale, if less than 3 items are missing then the aggressive behavior subscale score will be imputed by replacing the missing item with the mean of the non-missing values (rounded to the nearest integer) for that subject and timepoint within

aggressive behavior subscale. If more than 2 items are missing then the aggressive behavior subscale score will be missing.

For the physically non-aggressive subscale, if only 1 item is missing then the physically non-aggressive subscale score will be imputed by replacing the missing item with the mean of the non-missing values (rounded to the nearest integer) for that subject and timepoint within physically non-aggressive subscale. If more than 1 item is missing then the physically non-aggressive subscale score will be missing.

For the verbally agitated behavior and hiding and hoarding subscales, if any of the items are missing then the subscale score will be missing.

5.2.2 Zarit Burden Interview (ZBI)

The ZBI is assessed at Baseline, Weeks 2, 4, 8 and 12/ET visits.

The ZBI was designed to assess the stresses experienced by caregivers of patients with dementia. Caregivers are asked to respond to a series of 22 questions about the impact of the patient's disabilities on their life. For each item, caregivers are to indicate how often they felt that way (never, rarely, sometimes, quite frequently, or nearly always) (0-4). The total score of ZBI will range from 0 to 88, with higher scores denoting more stresses experienced by caregivers. If there are less than 5 missing items then the total score will be imputed by replacing each missing item with the mean (rounded to the nearest integer) of the non-missing values for that subject and timepoint. If there are more than 4 missing items then the total score will be missing.

If the informant of ZBI is a professional caregiver, their ZBI total scores will not be included in the summaries.

5.2.3 Alzheimer's Disease Cooperative Study – Activities of Daily Living Inventory (ADCS-ADL)

The ADCS-ADL is assessed at Baseline and Week 12/ET visits.

The ADCS-ADL is an inventory to assess activities of daily living (ADL) in subjects with AD. This is a caregiver-rated 23-item questionnaire, with sub-questions and sub-items for some items, including both basic (e.g. personal hygiene, eating, bathing) and instrumental (e.g. preparing a meal, using a telephone) ADLs. The recall period for this questionnaire is 4 weeks. The total score can range from 0 to 78, with lower scores indicating worse functioning.

A response of “DON’T KNOW” is not considered a missing value, rather it will be scored similarly to a “NO” response (i.e., that item score will be set to 0). The following table includes the item score range and the scoring rule. These rules will only apply in the analysis dataset; the raw data values will remain unchanged.

Table 2 ADCS-ADL Item Score Range

Item Number	Score Range	Note*
1-5, 8-12, 14, 17-19, 21, 22	0-3	For item 8, the score is sum of 8A, 8B, and 8C. The sub-question will be equal to 0 if the main or sub-question checks NO or DON’T KNOW. For item 18, the score is sum of 18A, 18B, and 18C. The sub-question will be equal to 0 if 1) the main or sub-question checks NO or DON’T KNOW; or 2) “patient is institutionalized” box is checked. For item 22, if NO or DON’T KNOW is checked then assign item score = 0. If YES is checked and one or more sub-item is checked, but the sub-question is not answered, then assign item score = 1. Otherwise, item score is equal to the non-missing sub-question score.
6	0-7	Sum of 6A (0-3; 0 if the main question checks NO or DON’T KNOW) and 6B (0-4).
7	0-5	
13, 15, 16, 23	0-4	For item 16, the score is sum of 16A (0-3; 0 if the main question checks NO or DON’T KNOW) and 16B (0-1; 0 if the main or sub-question checks NO or DON’T KNOW). For item 23, if NO or DON’T KNOW is checked then assign item score = 0. If YES is checked and one or more sub-item is checked, but the sub-question is not answered, then assign item score = 1. Otherwise, item score is equal to the non-missing sub-question score.
20	0-2	

* Item 7-21. If NO or DON’T KNOW is checked, then assign item score = 0. If YES is checked, the score of the item is sum of non-missing score(s) of the sub-question(s).

In addition to the total score, the following subscale scores will be defined:

- Basic subscale score: 6 Items (minimum = 0, maximum = 22)
Sum of scores from items 1, 2, 3, 4, 5, 6
- Instrumental subscale score: 17 Items (minimum = 0, maximum = 56)
Sum of scores from items 7, 8, 9, 10, 11, 12, 13, 14, 15, 16, 17, 18, 19, 20, 21, 22, 23

After applying the preceding data handling rules, if missing values remain then the 23-item total, basic, and instrumental scores will be derived as follows:

For the 23-item total score, if the sum of the maximum possible scores among all of the missing items is less than or equal to 16 then the total score will be derived as 78 multiplied by (sum of observed item scores divided by the sum of maximum possible scores among observed items), rounded to the nearest integer. Otherwise, the total score will be missing.

For the basic subscale score, if the sum of the maximum possible scores among the missing items is less than or equal to 4 then the basic subscale score will be derived as 22 multiplied by (sum of observed basic item scores divided by the sum of the maximum possible scores among observed basic item scores), rounded to the nearest integer. If the sum of the maximum possible scores among the missing items is greater than 4 then the basic subscale score will be missing.

For the instrumental subscale score, if the sum of the maximum possible scores among the missing items is less than or equal to 11 then the instrumental subscale score will be derived as 56 multiplied by (sum of observed instrumental item scores divided by sum of the maximum possible scores among observed instrumental item scores), rounded to the nearest integer. If the sum of the maximum possible scores among the missing items is greater than 11 then the instrumental subscale score will be missing.

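### ADCS-ADL items 8, 16 and 18: a blank sub-question under a YES answer scores as 0 and escapes the SAP's proration, so a blank at one visit can create a false change of 1 to 3 points

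*SAP*

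**What the plan says.** All the scoring rules are in SAP Section 5.2.3.

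- **YES items, 7 to 21** (Table 2 footnote): "If YES is checked, the score of the item is sum of non-missing score(s) of the sub-question(s". NO or DON'T KNOW gives 0.
- **Items with several parts.** "For item 8, the score is sum of 8A, 8B, and 8C"; "For item 18, the score is sum of 18A, 18B, and 18C"; each has an item maximum of 3. Item 16 is 16A (0-3) plus 16B (0-1), maximum 4.
- **Items 22 and 23** have their own rule: "If YES is checked and one or more sub-item is checked, but the sub-question is not answered, then assign item score = 1".
- **Proration comes last.** "After applying the preceding data handling rules, if missing values remain then the 23-item total, basic, and instrumental scores will be derived as follows". The total is then "78 multiplied by (sum of observed item scores divided by the sum of maximum possible scores among observed items", rounded, provided the missing items' maxima sum to at most 16. The instrumental subscale works the same way on 56 points with a limit of 11.

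The scale runs from 0 to 78, lower meaning worse function, and is taken at Baseline and Week 12/ET. SAP Section 13.3 analyses the change by ANCOVA, once with LOCF and once with observed cases. Protocol Section 9.6 leaves instrument scoring to the SAP.

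**The concern.** The SAP separates two situations: DON'T KNOW is an answer worth 0, and a blank is missing. For one part of item 8, 16 or 18 the footnote removes that distinction, because a part left out of the sum contributes the same as a part scored 0. The item then has a score, so nothing remains missing. It is not prorated, and the blank does not count toward the 16- or 11-point limit.

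Elsewhere the SAP fills limited blanks from the answered items (CMAI total, ZBI, NPI-C and MMSE, Sections 5.2.1, 5.2.2, 5.2.4 and 5.2.7). It gives no reason for a different approach here.

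ADCS-ADL is the instrument for the functional-status objective and has only two assessments. A blank at Week 12 alone looks like decline, and a blank at Baseline alone looks like improvement. The LOCF and observed-case analyses use the same derived total, so comparing them would not reveal it.

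**Working it through.** **1. Reproduce the plan's maxima from Table 2.**
- Basic (items 1-6): 5×3 + 7 = 22.
- Instrumental (items 7-23): 5 + 15 + 4 + 3 + 4 + 4 + 9 + 2 + 3 + 3 + 4 = 56, taking item 7, items 8-12, 13, 14, 15, 16, items 17-19, 20, 21, 22 and 23 in order.
- Total: 22 + 56 = 78, as stated.

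**2. Size of the false change.** For a subject whose function is unchanged, it equals the true score of the blank part. Take a subject at the same fraction of maximum on every item, ignoring rounding:

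| Fraction of maximum | 16A blank | One-point part blank | Whole item missing (prorated) |
|---|---|---|---|
| 40% | -1.2 | -0.4 | 0 |
| 60% | -1.8 | -0.6 | 0 |
| 80% | -2.4 | -0.8 | 0 |
| 100% | -3.0 | -1.0 | 0 |

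With one part answered in each of items 8, 16 and 18, the largest loss is 2 + 3 + 2 = 7 of 78 (9.0%). Table 2 gives 16A as 0-3 and 16B as 0-1. The 0-1 range for each part of items 8 and 18 is inferred from three parts sharing a maximum of 3.

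**3. Worked totals.** Sub-question proration here means 78 × (all answered points) / (78 - maximum of the blank part).

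| Case | True total | SAP rule | Whole item set to missing | Sub-question proration |
|---|---|---|---|---|
| A. Other items 47/74; 16A blank (truly 2), 16B = 1 | 50 | 47+1 = 48 | 78×47/74 = 49.5 → 50 | 78×48/75 = 49.9 → 50 |
| B. Other items 47/75; 8A = 8B = 1, 8C blank (truly 1) | 50 | 47+2 = 49 | 78×47/75 = 48.9 → 49 | 78×49/77 = 49.6 → 50 |
| C. Other items 30/74; 16A = 3, 16B blank (truly 1) | 34 | 30+3 = 33 | 78×30/74 = 31.6 → 32 | 78×33/77 = 33.4 → 33 |
| D. Other items 47/74; 16A = 3, 16B blank (truly 0) | 50 | 47+3 = 50 | 78×47/74 = 49.5 → 50 | 78×50/77 = 50.6 → 51 |

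Case A shows the artefact: a partial answer gives an error of -2, while leaving all of item 16 blank gives none. Cases B and C show that discarding the whole item can do no better than the SAP rule, or worse. Case D shows that sub-question proration is not exact for every subject either.

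**4. Where the wording is unclear.** Items 7, 9-15, 17 and 19-21 are read as having a single sub-question, because Table 2 names no parts for them. They hold 5 + 12 + 4 + 3 + 4 + 3 + 3 + 2 + 3 = 39 of the 78 points. If YES is checked and that sub-question is blank, the sum is empty, and the SAP does not say whether this is 0 or missing. With item 7 truly 4 and other items 46/73 (true total 50), reading it as 0 gives 46. Reading it as missing gives 78×46/73 = 49.2, rounded to 49.

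**5. Arm level.** 111/3 = 37 subjects per arm. One affected subject moves the raw mean change by 1/37 = 0.03 (1 point) or 3/37 = 0.08 (3 points). The documents give no frequency of blanks. If 1% to 10% of an arm's subjects were affected at one visit (an assumption), the shift would be 0.01 to 0.10 for a 1-point loss and 0.03 to 0.30 for a 3-point loss.

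**The case against.** The strongest reply is that this is a prespecified imputation convention, the same in every arm, and that no convention is right for every subject. Cases C and D bear that out. Setting the whole item to missing throws away answers and can be further from the truth than the SAP rule. This stands as an objection to whole-item deletion, and it is why the fix works at sub-question level.

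It also stands that nothing suggests blanks differ by arm. Caregivers are blinded, so the expected effect on the treatment difference is mainly noise. Protocol Section 8.1 requires omissions on the eCRF to be explained, and Table 2 offers a DON'T KNOW response, scored 0, for the parts of items 8 and 18 and for 16B. Blanks may therefore be few. The sample form in protocol Appendix K was not available for this check.

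The reply does not remove the point. For items 8, 16 and 18 the derived visit score can never exceed the true one, and the SAP's own remedy for missing data is bypassed.

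A reader might add items 22 and 23, where (3-1) + (4-1) = 5 further points give 12 of 78 (15.4%). The documents do not support putting these in the same class. Those items receive an explicit value of 1, not 0, and that value is exact when the true score is 1. The 12-point figure also needs five items partly blank at one visit.

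**Conclusion.** The point holds for items 8, 16 and 18. Table 2 treats a blank part as 0 at the item's full maximum, while the proration rule covers only items still missing. A blank at one visit can create a false change of up to 1 point for a one-point part, up to 3 for 16A, and at most 7 of 78 over the three items. The last figure rests on a 0-1 range for each part of items 8 and 18. No false change arises if the true sub-score is 0 or equal points are lost at both visits.

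Two wider inferences should not be drawn:
- **That the error always shows worse function.** This is true of a single visit score on these three items. In the change score it can go either way.
- **That a partly answered item is in general handled worse than an unanswered one.** Case A shows it can be; case C shows the reverse.

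The practical weight is low: the endpoint is exploratory, the trial stopped at 111 subjects, no hypothesis testing is planned, and the frequency of blanks is unknown. The change is worth making because it is cheap and neither planned analysis would expose the artefact.

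**What to change.** In SAP Section 5.2.3, after the NO and DON'T KNOW rules:

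1. Treat an unanswered sub-question of item 8, 16 or 18 as missing. Keep the answered parts, remove only the blank part's maximum from the denominator, and count that maximum toward the existing limits. With M the summed maxima of missing items and blank parts, total = 78 × observed points / (78 - M) if M ≤ 16, and instrumental = 56 × observed points / (56 - M) if M ≤ 11.
2. State the maximum of each part of items 8 and 18, confirmed against the form.
3. Treat a YES item in 7-21 with no sub-question answered as a missing item, not as 0.
4. Leave the DON'T KNOW rule and the item 22/23 rule as they are.
5. Report the number of affected items by visit and arm.

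The cost is a few sentences and a small derivation change before database lock. Since the protocol leaves scoring to the SAP, no protocol text has to change. Occasionally a total or instrumental score will reach its missing limit. Blanks in items 8, 16 and 18 alone cannot cause this, because those items hold 3 + 4 + 3 = 10 points, below both 11 and 16.
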